
6 SELECTION AND WITHDRAWAL OF SUBJECTS

6.1 Inclusion criteria

To be eligible to participate in this study, all of the following criteria must be met:

1. An Institutional Review Board (IRB)/Independent Ethics Committee (IEC) approved written Informed Consent form is signed and dated by the subject.
2. Subject is considered reliable and capable of adhering to the protocol and visit schedule according to the judgment of the Investigator.
3. Subject completes all dosing requirements in PS0010 without meeting any withdrawal criteria and completes the study.

4. Female subjects of childbearing potential and male subjects with a partner of childbearing potential must continue to use an acceptable method of contraception (as detailed in PS0010) for up to 20 weeks after the last dose of study treatment in PS0011.

6.2 Exclusion criteria

Subjects are not permitted to enroll in the study if any of the following criteria are met:

1. Subject has previously participated in this study.
2. Female subjects who plan to become pregnant during the study or within 20 weeks following last dose of study medication. Male subjects who are planning a partner pregnancy during the study or within 20 weeks following the last dose.
3. Subject has any medical or psychiatric condition that, in the opinion of the Investigator, could jeopardize or would compromise the subject's ability to participate in this study. Note: For any subject with an ongoing serious adverse event (SAE), or a history of serious infections (including herpes zoster or hospitalizations) in PS0010, the Medical Monitor must be consulted prior to the subject's entry into PS0011.
4. Subject must have a negative interferon gamma release assay (IGRA) as measured at Week 8 of PS0010.
5. Any subject who meets any withdrawal criteria in the feeder study (PS0010) is excluded from participating in the extension study (PS0011).

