^a Visit windows of ±3 days from the first dose (Baseline) at all visits except SFU, which has a window of -3 and +7 days from scheduled visit date.

^b The SFU Visit will occur 20 weeks after the last dose of bimekizumab or placebo.

^c Ensure that the informed consent for PS0011 was completed by the subject during the Week 8 or Week 12 Visit of PS0010 (must be done before any study assessments are performed for PS0011).

^d To be performed prior to the first dose of bimekizumab or placebo in PS0011.

^e Includes evaluation of signs and symptoms of active TB and risk for exposure to TB.

^f The noted PS0011 Baseline assessments will be obtained at the Week 12 Visit of PS0010 and do not need to be recorded on the case report form for this study.

^g Vital signs (blood pressure, pulse rate, and temperature) are to be measured prior to blood sampling and prior to dosing, where applicable.

^h Pregnancy testing will be urine testing at all visits except SFU, which will be a serum test.

ⁱ It is recommended that the QuantiFERON TB GOLD test be performed.

^j Ensure that an IGRA test was performed during the Week 8 Visit of PS0010 and the result was negative.

^k All blood samples are to be taken prior to dosing.

^l Including assessment for the development of different forms of psoriasis at the SFU visit.

^m Subjects who received placebo or bimekizumab 64mg, 160mg, or 320mg loading dose + 160mg Q4W in PS0010 must achieve PASI90 response at Week 12 in PS0010 to enter the PS0011 extension study on the same treatment dose. Subjects who do not achieve PASI90 response at Week 12 in PS0010 while receiving placebo or bimekizumab 64mg will be assigned to receive bimekizumab 160mg on entering PS0011. Subjects who do not achieve PASI90 response at Week 12 in PS0010 while receiving bimekizumab 160mg or 320mg loading dose + 160mg will be assigned to receive bimekizumab 320mg Q4W on entering PS0011. Subjects who receive bimekizumab 320mg or 480mg Q4W in PS0010 will be assigned to receive bimekizumab 320mg Q4W on entering PS0011, regardless of their PASI90 response at Week 12 in PS0010. Any subject who does not achieve PASI75 response at Week 12 or later in PS0011 will be withdrawn from study treatment and will return to complete the Early Withdrawal Visit assessments.

[figure not shown]

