8.1 Baseline Visit

The Baseline assessments noted with an * will be obtained at the Week 12 Visit of PS0010 and do not need to be recorded on the eCRF for this study.

All procedures or assessments will be performed prior to administration of study drug, unless otherwise noted. The following procedures or assessments will be performed:

- Ensure that a separate Informed Consent Form was completed by the subject for PS0011 during the Week 8 or Week 12 Visit of PS0010 (must be done prior to any PS0011 study procedures)
- Confirm that a TB test (IGRA) was performed at the Week 8 Visit of PS0010 and the results were negative
- Assessment of inclusion/exclusion criteria
- Vital signs (blood pressure, pulse rate, and temperature)*
- Body weight*

-
- Physical examination*
 - Record 12-lead ECG*
 - eC-SSRS*
 - TB questionnaire*
 - PASI*
 - IGA*
 - DLQI*
 - BSA*
 - mNAPSI*
 - PSSI*
 - PGADA*
 - SF-36*
 - HADS*
 - Obtain blood samples for:
 - Standard safety laboratory tests (hematology and biochemistry)*
 - Bimekizumab plasma concentration*
 - Anti-bimekizumab antibodies*
 - Obtain urine sample for:
 - Standard safety laboratory tests (urinalysis)*
 - Urine pregnancy test for women of childbearing potential*
 - Concomitant medications
 - Record AEs
 - Contact the IXRS
 - Study medication administration (after all other visit assessments are completed)

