9.8 Other safety measurements

9.8.1 Assessment and management of TB and TB risk factors

All subjects will be assessed for TB through physical examination for signs and symptoms of TB, laboratory testing ([Section 9.8.1.1](#)), and subject questionnaire ([Section 9.8.1.3](#)). A chest x-ray can be performed in PS0011, if warranted, to confirm or exclude TB ([Section 9.8.1.2](#)).

At the Baseline Visit of PS0011, all subjects will undergo physical examination for signs and symptoms of TB and must be confirmed to have undergone an IGRA test (QuantiFERON TB GOLD is recommended) at the Week 8 Visit of PS0010 with negative results. In addition, each subject will complete a TB questionnaire with questions directed at symptoms of TB and potential exposure to TB.

Exclusion criteria at Baseline of PS0011

Subjects with known TB infection, at high risk of acquiring TB infection, or latent TB infection are excluded.

- a. Known TB infection whether present or past is defined as:
 - Active TB infection or clinical signs and symptoms suspicious for TB (pulmonary or extra-pulmonary)
 - History of active TB infection involving any organ system or findings in other organ systems consistent with TB infection, unless adequately treated and proven to be fully recovered upon consult with a TB specialist
 - Any evidence by radiography or other imaging modalities consistent with previously active TB infection that is not reported in the subject's medical history
- b. High risk of acquiring TB infection is defined as:
 - Known exposure to another person with active TB infection within the 3 months prior to enrollment
 - Time spent in a healthcare delivery setting or institution where individuals infected with TB are housed and where the risk of transmission of infection is high
- c. Latent TB infection is defined as:
 - The absence of signs, symptoms (ie, evidence of organ-specific involvement), or physical findings suggestive of TB infection with a positive IGRA test (or 2 indeterminate IGRA test results) and a chest x-ray (or other imaging) without evidence of TB infection. If the result of the IGRA test is indeterminate, the particular IGRA test previously performed may be repeated once; if positive or indeterminate on retest, the subject may not be enrolled in the study. The retest must be done prior to entry in PS0011.

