Note: If available, respiratory or other specimens must also be smear and culture negative for TB (Centers for Disease Control diagnosis of LTB infection)
<http://www.cdc.gov/TB/topic/testing/default.htm>
- d. Current or history of NTMB infection

Signs and Symptoms

The Investigator should consider all potential sites of infection when assessing for TB during the physical examination and other evaluations, and based on the subject's medical or social history.

The most common primary focus of TB is the lung. Other sites may include GI system, bone/joints, lymph glands and meninges, etc. However, in immune compromised patients and/or patients treated with TNF inhibitors, extrapulmonary manifestations of TB are common compared to the normal population.

Some common symptoms that the subject may present are dependent on the primary focus of infection and may include cough, blood in sputum, night sweats, lymphadenitis, joint pain/swelling, spinal deformity, headache/confusion, abdominal pain (mimicking inflammatory bowel disease), etc. Unusual presentations should always be considered.

Latent TB infection is defined in the “Exclusion Criteria” above. If the result of the IGRA is indeterminate, the particular IGRA previously performed may be repeated once; if positive or indeterminate on retest, the subject may not be enrolled in the study without further evaluation by a TB specialist. In the event of an indeterminate test result, the retest must be done prior to the next visit. If LTB infection or active TB is identified, subject must undergo appropriate study specified withdrawal procedures. Laboratory diagnosis should be undertaken via mycobacteria culture media (or if available by preferred nucleic acid amplification test such as the Xpert MTB RIF test) and the result must be negative for TB inducing pathogens.

Test Conversion

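### Protocol Section 9.8.1 contradicts itself on entry after an indeterminate IGRA, and the entry checks in Section 6.2, Section 8.1 and Table 5-1 make no provision for the repeat test it allows

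*Protocol*

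**What the plan says.** Four places in the protocol state the IGRA condition for entering PS0011 without mentioning a repeat:

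- Section 6.2, exclusion criterion 4: "Subject must have a negative interferon gamma release assay (IGRA) as measured at Week 8 of PS0010". It stands under the stem "Subjects are not permitted to enroll in the study if any of the following criteria are met".
- Section 5.2, Table 5-1 footnote j: "Ensure that an IGRA test was performed during the Week 8 Visit of PS0010 and the result was negative".
- Section 8.1, Baseline Visit: "Confirm that a TB test (IGRA) was performed at the Week 8 Visit of PS0010 and the results were negative".
- The opening of Section 9.8.1 likewise asks for confirmation of a negative Week 8 result.

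Section 9.8.1 then deals with an indeterminate result in two paragraphs:

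- Item c of its block of Baseline exclusion criteria lets the test be repeated once, and then: "if positive or indeterminate on retest, the subject may not be enrolled in the study. The retest must be done prior to entry in PS0011". The same item counts two indeterminate results alongside a positive one in defining latent TB. The block opens with "Subjects with known TB infection, at high risk of acquiring TB infection, or latent TB infection are excluded".
- The paragraph under Signs and Symptoms also allows one repeat, but says that a subject who is positive or indeterminate on it "may not be enrolled in the study without further evaluation by a TB specialist". It sets the retest deadline as before the next visit, as Section 9.8.1.1 also does.

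**The concern.** This check decides who starts up to 48 weeks of blinded treatment with an immunomodulator, and Section 9.6 lists TB among the events for special monitoring. An entry rule at that point should give one answer for each test history. Here two sites, each following the protocol's text, could reach opposite decisions on the same subject. Monitors would then have no firm basis for classifying either decision as a protocol deviation.

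**Working it through.** No arithmetic applies and there is no stated figure to reproduce. The check takes each possible IGRA history through the current text; the amendment log was not used. *Short checks* means criterion 4 as intended, footnote j and Section 8.1.

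| Week 8 result, then repeat | Short checks | 9.8.1 item c | 9.8.1 Signs and Symptoms |
|---|---|---|---|
| Negative, none needed | Eligible on IGRA | Eligible on IGRA | Eligible on IGRA |
| Indeterminate, then negative | Refused: the Week 8 result was not negative | Not barred | Not barred |
| Indeterminate, then indeterminate | Refused | Refused, no exception | Barred only until a TB specialist has evaluated |
| Indeterminate, then positive | Refused | Refused, no exception | Barred only until a TB specialist has evaluated |

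1. **Repeat positive or indeterminate.** The two paragraphs of 9.8.1 share the words "if positive or indeterminate on retest, the subject may not be enrolled in the study". Item c ends the sentence there. Signs and Symptoms goes on to add the specialist condition. The first is an absolute bar and the second a conditional one, for the same subject. Under item c, two indeterminate results with clear imaging and no signs or symptoms are latent TB, which is itself an exclusion.

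2. **Repeat negative.** The short checks name the Week 8 test and its result. A later repeat is not that test, so on their wording the subject fails. Item c provides for a repeat before entry and attaches no bar to a negative one. The opening of 9.8.1 sides with the short checks, so this conflict also lies partly inside that section.

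3. **Retest deadline.** Item c says before PS0011 entry; Signs and Symptoms and Section 9.8.1.1 say before the next visit. PS0011 Baseline is the PS0010 Week 12 Visit, so the two coincide if Week 12 is the next visit after Week 8. The PS0010 visit schedule is not in these documents, so this cannot be confirmed.

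All three retest sequences therefore lack a single outcome: one because the short checks differ from 9.8.1, two because 9.8.1 differs from itself.

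**The case against.** The strongest reply is that the text can be read together. On that reading the short checks state the general requirement and item c says how an indeterminate result is resolved; none of the short checks forbids a repeat. The Signs and Symptoms sentence sets a necessary condition and does not grant entry. Its paragraph points back to the latent TB definition in the exclusion block and requires withdrawal procedures if latent TB is found. A site admitting a twice-indeterminate subject would be following one sentence against several others.

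Much of this is fair as a guess at intent. It does not remove the conflict. No section says which governs, and the short checks carry no pointer to item c. If the bar in item c is absolute, the specialist condition has no work to do.

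Two stronger readings are tempting, and the documents do not support them.

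- **That criterion 4 excludes subjects with a negative test.** Under its stem it says this literally. But footnote j, Section 8.1 and Section 9.8.1 all require a negative result, so the intent is plain. This is a drafting slip, unlikely to change who enters.
- **That subjects with TB exposure or an NTMB history pass entry because Section 6.2 does not name those exclusions.** The 9.8.1 block is headed as Baseline exclusion criteria and binds where it stands. Inclusion criterion 3 and exclusion criterion 5 bar anyone who met a PS0010 withdrawal criterion, and exclusion criterion 3 leaves room for investigator judgment. The Baseline TB questionnaire and physical examination both cover exposure. The PS0010 criteria are not in these documents, so how much they catch is unknown. What remains is a missing cross-reference: the only pointer from Section 6 to 9.8.1 is under withdrawal criterion 6.

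**Conclusion.** The concern holds for the indeterminate IGRA. Section 9.8.1 gives two different answers when the repeat is positive or again indeterminate. When the repeat is negative, the short checks and item c give different answers. The conclusion rests only on the current protocol wording.

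Its size cannot be derived, because the documents give no rate of indeterminate results. A reader might assume a rate of 1% to 5% and apply it to the 240 planned subjects, which gives 0.01 × 240 = 2.4 to 0.05 × 240 = 12. That range has no support in the documents. It also counts every first indeterminate result, whereas the contradiction inside 9.8.1 needs a second non-negative one.

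Two further inferences should not be drawn.

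- **The IGRA interval.** PS0010 Week 8 to PS0011 Week 48 is 4 + 48 = 52 weeks without a scheduled IGRA. That concerns test frequency, not the entry rule, and TB questionnaires are scheduled at Baseline and Weeks 12, 24, 36 and 48.
- **The primary safety result.** The Safety Set is everyone dosed in PS0011 and the primary variable covers all treatment-emergent adverse events. No planned estimate is shown to change.

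**What to change.** Reconcile Table 5-1 footnote j, Section 6.2 criterion 4, Section 8.1, both paragraphs of Section 9.8.1 (with its opening requirement) and Section 9.8.1.1 into one TB entry rule. It should state:

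- a single outcome for each of indeterminate then negative, indeterminate then indeterminate, and indeterminate then positive;
- one retest deadline.

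Which outcome applies in each case is for the sponsor's clinical team.

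Two minor edits should go with it: reword criterion 4 in exclusion form, and cross-reference the 9.8.1 Baseline exclusions (known TB, high risk, latent TB, NTMB) from Section 6.2.

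The cost is protocol wording and an update to the eligibility eCRF page, through the usual amendment approval under Section 15.5 (sponsor, IRB/IEC and, where required, regulators). The reconciliation itself calls for no additional staff and no test beyond the repeat that the protocol already describes.

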6.3 Withdrawal criteria

Subjects are free to withdraw from the study at any time, without prejudice to their continued care.

Subjects should be withdrawn from the study and will be asked to complete the Early Withdrawal Visit and SFU Visit (20 weeks after the last received dose) if any of the following events occur:

1. Subject withdraws his/her consent.
2. There is confirmation of a pregnancy in a female subject during the study, as evidenced by a positive pregnancy test.
3. The Sponsor or a regulatory agency requests withdrawal of the subject.
4. Subject develops an illness that in the opinion of the Investigator would interfere with his/her continued participation if the risk of continuing participation outweighs the potential benefit.
5. Subject develops erythrodermic, guttate, or pustular form of psoriasis.
6. Subjects considered to have either a suspected new latent tuberculosis (LTB) infection or who develop an active TB or NTMB infection during the study (including but not limited to, conversion demonstrated by IGRA or other diagnostic means) must be immediately discontinued from study medication; an Early Withdrawal Visit must be scheduled as soon as possible, but not later than the next regular visit.

Confirmed active TB is an SAE and must be captured on an SAE Report Form and provided to the Sponsor in accordance with SAE reporting requirements. As with all SAEs, periodic

follow-up reports should be completed as per protocol requirements until such time as the TB infection resolves.

Additional information on TB policies are provided in [Section 9.8.1](#).

7. Subject is noncompliant with the study procedures or medications in the opinion of the Investigator.
8. Subject uses prohibited concomitant medications, with the exception of topicals, as defined in this protocol ([Section 7.8.2](#)), that may present a risk to the safety of the subject in the opinion of the Investigator and/or the Medical Monitor.
9. Subject has a clinical laboratory value meeting the following criteria:
 - Common Terminology Criteria for Adverse Events (CTCAE) Grade 3 and above: subjects must be withdrawn regardless of relationship to study drug or duration of event.
 - CTCAE Grade 2
 - Subjects may remain in the study if the event is transient. If a subject has a Grade 2 laboratory abnormality, a retest is required within 1 to 2 weeks at a scheduled or unscheduled visit. If the repeat value is below Grade 2, the subject may receive the next scheduled study treatment. If the value on the repeat is still Grade 2 or above, a second repeat test must be performed and results made available prior to the next scheduled study treatment. If this second repeat value is still Grade 2 or above, the subject must be withdrawn.
10. Subject has active suicidal ideation as indicated by a positive response (“Yes”) to questions 4 or 5 or to the suicidal behavior questions of the “Since Last Visit” version of the self-rated electronic Columbia-Suicide Severity Rating Scale (eC-SSRS). The subject should be referred immediately to a Mental Healthcare Professional and must be withdrawn from the study.
11. Subjects with a HADS-D score ≥ 15 must be withdrawn. Any subject who develops a HADS-D score of >10 during the study should be referred immediately to a Mental Healthcare Professional for further evaluation and potential withdrawal by the Investigator.
12. Subject does not achieve PASI75 at Week 12 or later following study treatment in PS0011.
13. Subject experiences an AE as described below:
 - Any CTCAE Grade 3 and above adverse event (AE) that is assessed as related to study drug in the opinion of the Investigator
 - If the event is deemed to be not related to study drug by the Investigator, the subject may remain in the study after approval by the Medical Monitor.
 - Any CTCAE Grade 2 event that is evaluated as related to study drug in the opinion of the Investigator, is persistent, and falls into any of the following System Organ Classes (SOCs): “Blood and lymphatic disorders,” “Cardiac disorders,” or “Vascular disorders.”
 - Persistent is defined as lasting 28 days or more, which spans at least 2 scheduled injections.

Investigators should attempt to obtain information on subjects in the case of withdrawal. For subjects considered as lost to follow-up, the Investigator should make an effort (at least 1 phone call and 1 written message to the subject), and document his/her effort (date and summary of the phone call and copy of the written message in the source documents) to complete the final evaluation. All results of these evaluations and observations, together with a narrative description of the reason(s) for removing the subject, must be recorded in the source documents. The eCRF must document the primary reason for withdrawal.

Investigators should contact the Medical Monitor, whenever possible, to discuss the withdrawal of a subject in advance.

